In phase II, after confirming the hypothesis that patients with pCIS tend to have poor outcomes as compared to the natural history of the disease, only patients with pCIS will be enrolled. 30 patients will be randomized into treatment including IAT or without IAT plus standard of care based on a simple 1:1 randomization. All otherwise IV tPA eligible patients will be treated with IVT using tPA regardless of the assigned group since this represents current standard of care. Based on previous studies, the results from Phase I should show poor results for pCIS patients, on the order of 15% good outcomes, below the published good outcomes for patients receiving no treatment. This phase will provide preliminary data to determine if IAT provides any benefit in these patients, or is even potentially harmful, which no other clinical trial to date of IAT has formally hypothesized or tested as plausible. Due to the low rate of success the investigators realize this phase will be underpowered to definitively show differences between two groups, but the phase will provide preliminary safety pilot data on a topic not studied to date to develop plans for a larger and adequately powered study.

All eligible patients participating in both phase I and phase II will be given the option to donate an additional 8.5 ml blood sample for genetic testing of the *Dce1* gene. Blood samples will be collected in Paxgene DNA tubes. Collection of this sample will occur during regularly scheduled blood work within 48-60 hours of admission. Akron General will store all samples until all patients are enrolled after which the samples will be sent to a biospecimen processing facility to identify polymorphisms of the *Dce1* gene. Results obtained from the genetic testing will be analyzed in conjunction with data from phase I and II.

The primary measure of outcome will be the same for both phases. The outcomes will be measured based on the modified Rankin Scale (see appendix) at least 3 months and again at 1 year following treatment. Patients will be graded according to this scale by an experienced

Version: 6.0

neurologist or other mRS scale certified health care provider not involved in the treatment and blinded to the treatment for each patient.

B. Study Population:

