Pre-operative condition and patients outcomes will be assessed using standardized and validated measures. The primary endpoint of a mRS score will be obtained at least 90 days following treatment and again at 1 year following treatment. NIHSS score will be obtained in the emergency room before the treatment, within 24 h of treatment, and before discharge. The person who will obtain the NIHSS will be certified to obtain it. Adequacy of revascularization will be assessed at the end of treatment by the treating physician according the modified thrombolysis in cerebral infarction (mTICI) scale (see Appendix). All of these measures are standards for care and trials of acute ischemic stroke. [8-10] All case report forms will be maintained by the primary investigator at the local site, and stored within locked cabinets. The personal identifying information on the case report forms will be deidentified and assigned a code before being transferred to Akron General Medical Center for transfer of the data to a de-identified database which will be used for analysis.

IV. DATA COLLECTION

Version: 6.0

A. How and what data will be collected

Data related to patient demographics, stroke risk factors, condition prior to treatment, time of treatment, and outcomes will be collected for each patient. Data on demographics will include sex, age, and race. Data on stroke risk factors will include history of hypertension, blood pressure, prior heart attack, arrhythmias, diabetes, glucose (sugar) level at admission, and obesity. Data on condition prior to treatment will include NIHSS score determined in the emergency room. Data on time of treatment will include time from symptoms to arrival at emergency room, time to start of DCA, and time to end of the procedure. Data on outcomes will include mRS at 3 months, mRS at 1 year, NIHSS score within 24 hours and at discharge, and complications brain edema and intra-cranial hemorrhage. Other parameters within these categories could be acquired as deemed necessary for analysis of the data.

V. DATA ANALYSIS

A. Sample Size Considerations

Phase I

A power analysis has been performed based on the previous retrospective analyses of the relationship between outcomes and the CIS for phase I. The sample size was calculated for the influence of the combination of CIS and revascularization on good outcomes (mRS \leq 2) based on the following assumptions.

- The percentage of patients with fCIS will be 60%

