- The percentage of patients with good revascularization will be 50%
- The rate of good outcomes for the combination of fCIS and good revascularization is assumed to be 70%
- The rate of good outcomes for the combination of fCIS and poor revascularization is assumed to be 20%
- The rate of good outcomes for the combination of pCIS and good revascularization is assumed to be 20%
- The rate of good outcomes for the combination of pCIS and poor revascularization is assumed to be 10%

The assumptions provide the following power analysis:

- $\alpha = 0.05$ for overall analysis and set to 0.025 for subgroup analysis comparing fCIS and good revascularization to all other groups due to multiple comparisons
- power = 0.90
- Needed Sample size = 54 patients
- An additional 6 patients completing the trial are budgeted due to risk of errors in estimated outcomes. An additional 15-20 patients are expected to be enrolled due to patients lost to the 90 day follow up and/or deviations from the protocol.

Phase II

Phase II will be an exploratory study evaluating the rates for good outcomes for patients with pCIS treated with IVT plus IAT vs. IVT (or other standard of care) only. The rate of good outcomes is expected to be approximately 13% for the IAT group with revascularization. The investigators have no prior data on expected rates of good outcomes for patients with pCIS treated with IVT only. The best possible outcome rate would be on

Version: 6.0

the order of 25% noted previously for untreated acute ischemic stroke. Due to the low levels of good outcomes, the investigators acknowledge the study will be underpowered to detect a difference between the two treatment groups for a total sample size of 30. Phase II will serve as a pilot study to initially establish estimates of rates of good outcomes for pCIS patients treated with IVT only for design of a larger prospective study.

Genetic Analysis

Genetic analysis will be performed based on the following:

- Genetic and expression analysis for the two groups based on their collateral score
- Adjust groups for cardiovascular/stroke risk factor presence and other known confounding conditions
- High density SNP array analysis will be performed for common and rare alleles
 against known collateral-related genes that have been identified in mice. These
 include human RABEP2 and its isoform RABEP1 and related gene pathways;
 VEGFA, FLK1 and their related gene pathways; NOTCH, DLL4, ADAM10,

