 ADAM17, CNX37 and their related gene pathways.
- Subgroup analysis will be performed for ethnicities.
- Taqman assays and/or exome sequencing of significantly associated SNPs and/or genes.
- Pending results, a future validation study will follow this discovery study by increasing the sample size.

B. Statistical Methodology

Data for the proposed study will be analyzed using comparison of proportions and multivariable logistic regression. Analysis of proportions based on Fisher exact tests will be used to compare rates of good outcomes between the fCIS and pCIS groups as the primary end point for phase I. The influence of successful revascularization on outcomes for patients with fCIS or pCIS will also be analyzed using Fisher exact tests as the secondary end point.

Binary and/or ordinal multiple logistic regression analyses will be used to evaluate the influence of multiple parameters on the likelihood of a good outcome. These parameters will include CIS, mTICI score, NIHSS score, time to revascularization, age, sex, history of diabetes mellitus, history of high blood pressure, history of coronary artery disease. The same analyses will be performed for phase II, instead focusing on the treatment groups rather than the CIS classification.

VI. DATA AND SAFETY MONITORING PLAN

A. Describe any provisions for monitoring the data for safety

A safety committee will monitor the data. The safety committee will be composed of at least 3 voting members. At least two members will be neurologists, neuroradiologists or neurointerventionalists with experience treating acute ischemic stroke who are not investigators at any of the sites. These members will not be affiliated with the institution of the principal investigator, any sub- investigator, or Akron General Medical Center. At least one member with a background in biostatistics who is not an investigator or affiliated with Akron General Medical Center will also be on the committee.

For phase I, the only deviations in normal standards of care are:

Version: 6.0

- 1- the extra few minutes for full DCA for some centers as opposed to injecting only the occluded vessel
- 2- Adding IAT to treatment of patients seen between 6 and 24 hours of onset of symptoms.

The safety committee will be looking at known potential complications for IAT in both fCIS and pCIS groups. These include:

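### Phase II's good-outcome comparison cannot register added death or severe disability within mRS 3-6, and no comparison of 90-day death or mRS 5-6 by arm is planned

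*Combined protocol and SAP*

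**What the plan says.** Section III.A gives Phase II a two-sided purpose: "This phase will provide preliminary data to determine if IAT provides any benefit in these patients, or is even potentially harmful". It also describes the phase as a safety pilot. Section VIII.B names the feared harm of IAT in pCIS patients: edema, hemorrhagic transformation and herniation.

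The outcome is not adapted to that purpose. Section III.A states: "The primary measure of outcome will be the same for both phases". Section V.A defines good outcome as mRS 2 or less and describes the phase this way: "Phase II will be an exploratory study evaluating the rates for good outcomes for patients with pCIS". Its planning rates are "The rate of good outcomes is expected to be approximately 13% for the IAT group with revascularization" and, for the arm without IAT, "The best possible outcome rate would be on" "the order of 25% noted previously for untreated acute ischemic stroke".

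Section V.B makes Fisher exact tests on good-outcome rates the Phase I primary analysis. It adds logistic regression, binary and/or ordinal, for the likelihood of a good outcome with nine listed parameters. For Phase II it says only: "The same analyses will be performed for phase II, instead focusing on the treatment groups rather than the CIS classification".

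On safety, Section VI lists two items for the committee, a defined type of hemorrhage and an NIHSS rise of 4 or more, each within 24 hours of treatment. In Phase II the committee compares complications and good outcomes between arms after 10 and 20 subjects. Section IV.A also collects brain edema, intracranial hemorrhage, and mRS at 3 months and 1 year.

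**The concern.** The harm that the protocol fears would act mainly on patients who are already doing badly. A patient who would have survived at mRS 4 but dies of herniation moves from 4 to 6. Both values count as not a good outcome, so the Fisher comparison is unchanged. This follows from the definition of the endpoint and would be true at any sample size.

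Phase II is also meant to supply planning data for a larger trial. If only good-outcome rates are reported by arm, that trial's designers would have no prespecified estimate of mortality, severe disability or shift across the scale, although the values will be in the database.

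**Working it through.** **Inputs from the documents.** 30 patients, 1:1 (III.A), taken as 15 per arm; simple randomization does not guarantee this split. Good outcome with IAT is about 13%, stated for IAT with revascularization (V.A). For all treated pCIS patients, the Phase I assumptions give 0.5 × 20% + 0.5 × 10% = 15%, which agrees with III.A. Without IAT the rate is at best 25% (V.A); the Background gives about 20% for untreated patients. The plan has no calculated figure for Phase II to reproduce.

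**Step 1: share of patients inside the blind category.** With IAT: 1 − 0.13 = 87%, or 1 − 0.15 = 85%. Without IAT: at least 1 − 0.25 = 75%.

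**Step 2: what the Fisher test can see when good outcome does change.** Exact power is the sum of Bin(i; 15, p1) × Bin(j; 15, p2) over all tables (i, j) with two-sided p ≤ 0.05.
- 13% vs 25%: power 5.7%.
- 0/15 vs 4/15: p = 0.0996. 0/15 vs 5/15: p = 0.042. With no good outcomes under IAT, significance therefore needs 5/15 = 33% without IAT, above the plan's best case.

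This step only puts a figure on the low power that the plan already admits.

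**Step 3: harm confined to mRS 3-6.** The documents give no death rates or mRS distribution, so what follows is assumed. For mRS 0 to 6 without IAT, take 3/7/10/15/25/15/25%. Good outcome is 3 + 7 + 10 = 20%, mRS 3-5 is 55% and death is 25%. With IAT, deaths rise to 50%, good outcome stays at 20% and mRS 3-5 falls to 30%.

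| Analysis, 15 per arm, two-sided 0.05 | Rejects in |
|---|---|
| Fisher on mRS 2 or less (20% vs 20%) | 1.7%, its false-positive rate |
| Fisher on death (25% vs 50%) | 15.7% |
| Wilcoxon-Mann-Whitney, added deaths drawn proportionally from mRS 3-5 | about 16-17% |
| Wilcoxon-Mann-Whitney, added deaths drawn from mRS 4-5 only | about 12-13% |

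The Fisher figures are exact. The others come from 8,000 simulated trials each, with and without continuity correction; the null rejection rate was about 5%.

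**Step 4: a second set of assumptions.** Deaths 20% without IAT; good outcome equal in both arms, at 13% or 25%; the remaining patients spread evenly over mRS 3-5.

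| Deaths with IAT | Fisher, mRS 2 or less | Fisher, death | Ordinal test | Per arm for 80% power on death |
|---|---|---|---|---|
| 35% | 1.0-1.8% | 6.9% | 8-9% | 138 |
| 50% | 1.0-1.8% | 24.6% | 20-24% | 39 |
| 60% | 1.0-1.8% | 44.7% | 31-40% | 23 |

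**Step 5: precision.** Exact (Clopper-Pearson) 95% limits at n = 15 are 1.7-40.5% for 2/15, 7.8-55.1% for 4/15 and 26.6-78.7% for 8/15. Deaths of 4/15 vs 8/15, close to 25% vs 50%, would be visible in a table, but the intervals overlap widely.

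**Step 6: the other planned looks at harm.**
- The two listed safety items end at 24 hours.
- The only stated stopping criterion compares pCIS with fCIS patients. Phase II enrolls only pCIS patients, so the criterion has no comparator there.
- Edema and hemorrhage are collected, but Section V.B names no analysis of them.
- The ordinal model is one of two permitted options, is multivariable and is worded toward a good outcome.

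None of these is a planned comparison of 90-day death or mRS 5-6 by arm.

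**The case against.** **The plan does look at harm.** A reader might infer that extra deaths and severe disability would go unseen in this trial. The documents do not support that. The mRS runs to 6 (dead) and is recorded at 3 months and 1 year; edema and hemorrhage are collected; the committee compares complications between arms twice; and ordinal regression is allowed. What stands is narrower: the good-outcome comparison is blind to this harm, and the other routes are short-term, optional or unspecified.

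**It is a declared pilot.** The plan says several times that Phase II is underpowered and wants estimates of good-outcome rates. For that aim mRS 2 or less is the right quantity and should stay. The plan does not rank a lead Phase II analysis, and nowhere does it say that a null result would mean no harm. Its admission concerns sample size, however, not what the endpoint can register.

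**Good outcome is itself a harm signal.** The Background raises harm because 13% lies below about 20% for untreated patients. The planned test addresses that version, though weakly. Step 3 holds good outcome fixed on purpose, to isolate the other version.

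**The ordinal test is no cure.** In Step 3 it misses the harm in more than 80% of trials. If 10 percentage points move only from mRS 5 to 6, it rejects in about 5%, its null level. If IAT raised both good outcomes (20% to 35%) and deaths (25% to 45%), it rejects in about 6%, because the shifts largely cancel. This stands. It is why death and mRS 5-6 must be shown separately, and why replacing the good-outcome rate would be a matter of preference.

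**Conclusion.** The point holds in limited form. Phase II asks about harm, but its one fixed outcome comparison by arm cannot register harm within mRS 3-6, where about 75% or more of each arm is expected. That rests only on the plan's own rates and the definition of the endpoint. The rejection rates (1.7% against about 12-17% and about 16%) rest on assumed mRS distributions and an even 15/15 split. Their size changes with those assumptions; the blindness of the dichotomy does not.

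Adding the missing comparisons would make such harm visible in the report. It would not turn 30 patients into a test of it. This is an inexpensive improvement that should be made, not a flaw that invalidates the phase.

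**What to change.** In Section V.B, extend the Phase II sentence. Keep the mRS 2-or-less rate per arm as the planning estimate, with an exact 95% CI, and prespecify beside it:

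- (a) an unadjusted comparison of the full 90-day mRS between randomized arms by Wilcoxon-Mann-Whitney, reported as an effect size with 95% CI;
- (b) 90-day death and mRS 5-6 by arm, with an exact 95% CI for each rate and a CI for the difference;
- (c) a statement that these are estimates and that a non-significant result is not evidence of no benefit or no harm.

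Separately, the stopping criterion in Section VI and the all-pCIS design of Phase II need to be reconciled by the protocol team.

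Cost: wording and slightly more analysis, with no new visits, data or patients. Phase II reporting would no longer mirror Phase I exactly.

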of good outcomes for these recent trials in the IAT arms have varied widely (52-71%). The investigators believe that a primary factor explaining differences between studies is the portion of people with favorable CIS included in the studies. Interestingly the ratio between the rate of good outcomes in the treatment arm vs. the control arm (no IAT) has been stable across the different positive trials showing the effect of IAT at approximately 1.7 for all of these recent trials, similar to the PROACT II trial more than 15 years ago. [3]. The investigators believe the stagnation of this ratio at 1.7 is evidence that the selection criteria have not improved despite improvement in the rate of revascularization. Based on the existing data, the investigators would like to evaluate the merit of CIS as a primary tool for patient selection in IAT, hoping to prove that the rate of treated to untreated improvement is on the order of 6 to 7. We expect that if we select for patients with fCIS and obtain good revascularization to obtain around 80% GCO in the treated arm. We also expect successful revascularization to be futile for patients with pCIS.

E. The principal investigator believes that the CIS for each patient is determined genetically. In order to explore the genetic link to the CIS, this trial also aims to perform SNP-trait association analysis to identify the genetic loci linked to CIS and stroke outcome in patients suffering from AIS. *Dce1* has recently been found to be responsible for approximately 85% of the variation in collateral extent and it is likely that polymorphisms of *Dce1* are a major determinant of the wide variation in collateral scores in humans. If it is shown that *Dce1* is correlated to CIS and both are predictive outcomes for EVT, then this will further increase confidence in CIS as an assessment of collateral status, strengthen patient stratification of patients to define course of treatment for best outcome and least risk, and suggest the use of genetic testing in clinical decision making.

II. STUDY OBJECTIVE(S); INCLUDING SPECIFIC AIMS AND/OR HYPOTHESES

The hypothesis, or idea being tested, is that as long as patients have a favorable CIS they can be successfully treated with IAT out to 24 hours. For patients with poor CIS, success rates will be relatively low, with no benefit provided by IAT. The long term objective is to:

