- a. Lengthen the time window of treatment for patients with fCIS from 6 hours to 24 hours. In doing so, we will offer useful treatment to patients who would otherwise be denied treatment under current standards.
- b. Encourage focusing on achieving good revascularization rather than limiting time during IAT for patients with fCIS.
- c. Improve the percentage of good outcomes in the treated population
- d. Save patients with pCIS from complications due to brain edema and intra-cranial hemorrhage that could potentially result from IAT
- e. Save the health care system the costs of futile treatment of patients with pCIS.

III. METHODS

A. Study Design:

Version: 6.0

The current study focuses on patients with acute ischemic stroke due to a blockage of the intracranial internal carotid artery or middle cerebral artery (M1). The study will be performed prospectively in up to 6 stroke centers. Akron General Medical Center is the primary institution for development of the study and data analysis for this multicenter trial. To participate in the study, all centers need to meet certain qualified requirements which include:

- One neurointerventionalist with 6 years' experience in performing IAT with multiple devices.
- Demonstrate coverage of the comprehensive stroke center 24 hours a day. The proposed study will be carried out over a period of 4 years from the initial approval date. Informed consent will be obtained for each patient, as described in section VIII. The study will be carried out in 2 phases (Figure 1).

Phase I will compare outcomes between treated patients with fCIS and pCIS. All eligible patients will be assessed by a full diagnostic cerebral angiogram with dye injection of all potential collaterals. DCA will be used to characterize the CIS. Treatment will be identical for both groups. All patients will be treated with the combination of IAT and the normal standard of care for a patient not receiving IAT (which may include IVT, but not always). The sample size will be set to have 60 patients complete the trial. Distribution of fCIS and pCIS patients will not be forced, but the option to balance groups may be employed if the percentage for one group reaches 70%.

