The population for the study will be patients with anterior circulation acute ischemic stroke due to blockage of the intracranial internal carotid artery or middle cerebral artery (M1) within 8 hours of onset of symptoms. Typically, IAT is only offered to patients up to 6 hours, with no treatment options directly targeting the clot available after that time. Occlusion of one of these vessels will be determined based on CT angiography, magnetic resonance angiography, or DCA. Only patients 18 or over will be considered for the study. Other inclusion criteria include a score of 8 or greater on the National Institute of Health Stroke Scale (NIHSS, see appendix). Exclusion criteria will include contra-indication for IAT found on initial CT, intracranial hemorrhage, stroke mimics (tumor, herpetic encephalitis, etc.), more than 1/3 hypodensity on non-enhanced head CT prior to intervention, ASPECT Score < 6, and pre-existing disability defined as mRS ≥ 2. Pregnant women will also be excluded.

[figure not shown]

Figure 1: Study design for Phase I

Version: 6.0 5

[figure not shown]

Figure 2: Study design for Phase II

C. Assessment of Resources

The multicenter study will be carried out at up to 6 stroke centers. Each center is expected to have approximately 1 patient per month eligible for the study. Enrollment of patients will be performed at the end of imaging at each institution. At Akron General Medical Center, consent will be obtained within the DCA imaging suite. Consent will be obtained by a person qualified by the local IRB other than the treating physician. At Akron General, consent will be acquired by one of two neurointerventional lab nurses. One of these two nurses is required to be present for treatment of each patient with acute ischemic stroke, regardless of participation in a study. These nurses are familiar with all aspects of the proposed treatment methods and typical outcomes. The nurses will perform documented training on methods for obtaining consent and maintaining confidentiality of data obtained from subjects enrolled in research projects.

D. Study Procedures

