- A. parenchymal hemorrhage type 2 symptomatic or asymptomatic hemorrhagic transformation within the vascular territory of the index ischemic stroke within 24 hours of treatment
- B. Any neurological worsening (NIHSS increase of 4 points or more) within 24 hours of treatment.

The rate of complications will be assessed by the safety committee after evaluation of 20, 30 and 40 patients. The trial will be stopped for safety if the rate of brain edema and intracranial hemorrhage is significantly larger for the pCIS group than the fCIS group.

The safety committee will meet at the end of phase I and give its recommendation to launch phase two or not depending on their review. The primary reason not to launch phase II would be higher than expected good outcomes for the pCIS patients treated with EVT plus standard of care, giving the indication that IAT should not be withheld from patients during phase II. During phase II, the safety committee will review the data on complications as noted above and percentage of good outcomes after 10 and 20 subjects are evaluated for comparisons between the two treatment groups.

VII. STUDY LIMITATIONS

A. Potential Limitations of Procedures

The primary limitation for phase II is the small sample size. Due to the expected relatively low rates of good outcomes for pCIS patients regardless of type of treatment, the power will not be sufficient to establish whether or not treatment with IAT is beneficial for patients with pCIS. The study will, however, provide the preliminary data needed to plan for a future, larger prospective clinical trial. Potential limitations for the genetic component of this study include DNA damage due to improper handling or storage of blood samples. The Paxgene DNA tubes are designed to stabilize DNA in the blood. However, the tubes will only function properly if the instructions for inverting the tube multiple times and prompt shipment for storage at Akron General are followed.

VIII. ETHICAL CONSIDERATIONS

A. Informed Consent

Enrollment of patients will be performed in an imaging suite at each institution. Once eligibility is determined by the treating physician based on imaging, the consent process will be initiated by a study research coordinator or study nurse. These investigators are familiar with all aspects of the proposed treatment methods and typical outcomes and maintaining confidentiality of data obtained from subjects enrolled in research projects.

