- 5. Interval developing of significant vasogenic edema causing herniation and/or other sign of mass effect
- 6. Arterial access complications such as retroperitoneal hematoma, rectus muscle hematoma, or large groin hematoma more than 25 cm
- 7. Arterial venous fistula in the groin confirmed by ultrasound
- 8. Allergic reaction to dve

Each complication will be treated following the standard of care. Since the complications above are reported with these types of intervention, but there is no firm data to determine the accepted rate per operator, any center that has two or more events will be scrutinized and their technique will be evaluated by the principal investigator and safety committee. If a shortcoming is identified, guidelines will be provided for the center specific to the complications or the center could be dropped.

D. Benefits to Subjects

For phase I, patients who can be treated between 6 and 24 hours following onset of symptoms for acute ischemic stroke will be treated with IAT plus standard of care. Currently those patients are not offered IAT due to the belief that too much time has passed to restore tissue that has been deprived of the primary source of circulation. However, the new Extend IA trial proved that these patients could be treated. [4] The investigators believe that successful treatment beyond 6 hours with IAT is possible for patients with fCIS. In doing so we are offering a potentially useful treatment to patients who would otherwise not have the option.

E. Costs to Subject

Version: 6.0

Costs to the subjects will be standard costs for the treatment performed for acute ischemic stroke. Usual, customary, and reasonable treatment costs will be initially billed to the patients insurance, if applicable, with the patient responsible for any portion not paid by insurance in accordance with usual institutional policies. The protocol is based on standard techniques for treating acute ischemic stroke that can be applied to an individual patient based on the discretion of the treating physician.

F. Compensation to Subject

All patients who participate in the 90 day follow up visit will be compensated for parking and mileage expense up to a maximum of \$25. All patients who participate in the 1 year follow up visit will be compensated for parking and mileage expense up to a maximum of \$25.

F. Provisions for vulnerable subjects

Vulnerable subjects, children, pregnant women, and prisoners, will not be enrolled in the study.

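### Eligibility stops at 8 hours from onset, but the hypothesis, the safety plan and the benefits statement describe IAT out to 24 hours

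*Combined protocol and SAP*

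**What the plan says.** Section III.B defines the study population by blockage of the intracranial internal carotid artery or "middle cerebral artery (M1) within 8 hours of onset of symptoms". It adds that IAT is usually offered only up to 6 hours.

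Three other places use 24 hours:

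- Section II gives as the hypothesis the "idea being tested, is that as long as patients have a favorable CIS they can be successfully treated with IAT out to 24 hours".
- Section VI.A lists only two departures from standard care in Phase I. The second is "Adding IAT to treatment of patients seen between 6 and 24 hours of onset of symptoms".
- Section VIII.D says that in Phase I "patients who can be treated between 6 and 24 hours following onset of symptoms for acute ischemic stroke will be treated with IAT", together with standard care.

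Section II also has objective (a), "Lengthen the time window of treatment for patients with fCIS from 6 hours to 24 hours", which it places under the long-term objective.

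Section I.A gives a different account of standard care from III.B: IAT for patients arriving within 8 hours.

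**The concern.** An onset limit decides who may be enrolled, so two limits in one protocol describe two different trials. Take a patient at 12 hours. Under III.B that patient is not eligible and, by Section VIII.B, receives the institution's usual care, which at the lead center is supportive treatment. Under VI.A and VIII.D the same patient is a Phase I patient who receives an intracranial procedure.

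Two consequences follow, and they are alternatives. If III.B governs, the trial cannot speak to the later part of its own hypothesis. If VI.A and VIII.D govern, some enrolled patients are protocol violations. In either case the sections that describe the departure from standard care and the expected benefit do not match the eligibility rule. "The study will be performed prospectively in up to 6 stroke centers", so centers reading different sections in good faith could apply different limits.

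**Working it through.** **Step 1. The windows side by side.**

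| Section | Role | Window from onset | Event that ends the clock |
|---|---|---|---|
| III.B | eligibility | up to 8 h | not named |
| II, hypothesis | what is tested | out to 24 h | treated |
| VI.A | Phase I departure from standard care | 6 to 24 h | seen |
| VIII.D | Phase I benefit | 6 to 24 h | treated |
| I.A | standard care | up to 8 h | arrival |
| III.B, usual offer of IAT | standard care | up to 6 h | not named |

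III.B and VI.A/VIII.D overlap from 6 to 8 hours, so the latter two conflict with III.B only from 8 to 24 hours. No section provides an exception or a late-entry cohort.

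**Step 2. Could the choice of clock close the gap?** Section III.C says "Enrollment of patients will be performed at the end of imaging at each institution". Section III.D gives a typical 2 to 3 hours for the procedure. If the 8 hours runs to enrolment, treatment ends at about 8 + 2 = 10 to 8 + 3 = 11 hours. That is still far short of 24.

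**Step 3. Does the sample size depend on the window?** The inputs in Section V.A are 60% favorable CIS, 50% good revascularization, and good-outcome rates of 70%, 20%, 20% and 10%. The cell shares are 0.6 × 0.5 = 0.30 for each favorable-CIS cell and 0.4 × 0.5 = 0.20 for each poor-CIS cell.

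- The comparison is favorable CIS with good revascularization (rate 0.70) against everyone else.
- The pooled rate in the others is (0.30 × 0.20 + 0.20 × 0.20 + 0.20 × 0.10) / 0.70 = 0.12 / 0.70 = 0.171.
- The normal-approximation formula for two proportions, with two-sided alpha 0.025, power 0.90, allocation 0.70/0.30 and continuity correction, gives 16 in the first group and 54 in total.

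The stated 54 is reproduced, and time from onset does not enter it.

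**Step 4. Does the planned analysis use the window?** The Phase I primary analysis in Section V.B is a Fisher exact test of favorable against poor CIS. Time to revascularization appears only as one covariate in the regression. No comparison by onset window is planned, every Phase I patient receives IAT, and Section II sets no threshold for successful treatment.

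**Step 5. What would late entry yield if it were allowed?** The documents give no late-entry share. Assuming 10% to 30% of the 60 planned completers, there would be 6 to 18 late entrants. If 60% of these had favorable CIS, that is 3.6 to 10.8, or about 4 to 11 patients. Such numbers support description only.

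**The case against.** The strongest case on the other side is that little turns on the conflict. The primary comparison, the 54 and Phase II need nobody beyond 8 hours. The 24-hour clause would have no formal test under either window. Objective (a) is expressly long term. All of this stands, and it limits the damage.

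It does not remove the conflict. The long-term label covers the objectives, whereas the hypothesis sentence in Section II says what is being tested, and VI.A and VIII.D describe treatment given in this trial. Figures 1 and 2 are not available and may show a window, but a figure would not change the wording of III.B.

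A reader might infer more than the documents support:

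- **That the hypothesis beyond 8 hours gets no data, without qualification.** This is true only if III.B governs.
- **That widening III.B would test the 24-hour clause.** It would not, for the reasons in Step 4 of the working.
- **That the loss can be given as a share of the 6-to-24-hour extension.** Clock hours are not patients.
- **That III.B is the only eligibility text.** The vulnerable-subjects provisions in Section VIII also set exclusions. III.B is the only section with an onset limit.
- **That physicians have discretion over the window.** Consent begins "Once eligibility is determined by the treating physician based on imaging", which concerns imaging and the order of steps. Divergence between centers is a risk, not something the protocol permits.
- **That the wording on seen and treated sets rival clock definitions.** It may be loose prose, but III.B names no event, so one is still needed.

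**Conclusion.** The conflict is real in the current Version 6.0 text. It is an error in what is written, not a missing detail, because the eligibility rule and the description of Phase I treatment cannot both be followed for a patient at 8 to 24 hours.

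Under III.B the number of eligible entrants after 8 hours is zero by rule, and no statement about IAT after that time can be supported. Under VI.A and VIII.D such patients would be enrolled against III.B. How many patients this concerns is unknown. The effect on the primary comparison, on the 54 and on Phase II as planned is nil.

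The conclusion rests on reading III.B as the operative onset limit and on the removed figures not containing an exception.

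**What to change.** State one window, and the event it is measured to, in Sections II, III.B, VI.A and VIII.D. Section IV.A already collects times to emergency room arrival and to the start of the angiogram, so either could serve. The choice belongs to the sponsor and the clinical team.

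**Default: keep 8 hours.**

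- Restate the hypothesis in Section II as IAT up to 8 hours.
- Settle first whether standard care ends at 6 hours (III.B) or at 8 hours (I.A). If 6, then VI.A and VIII.D should refer to 6 to 8 hours. If 8, that interval is not a departure from standard care, and both statements should be removed.
- Say that long-term objective (a) is not tested in this trial, and draw no conclusion beyond 8 hours.

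This is a wording amendment with no change to sample size or analysis.

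**If 24 hours was intended.**

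- Correct III.B for Phase I only, and state the Phase II window separately. III.B covers both phases, so a plain change to 24 hours would also open the randomized phase to late entrants, whereas VI.A and VIII.D speak of Phase I alone.
- Recheck the 60% favorable-CIS share and the outcome rates behind the 54.
- Label any late-window results as descriptive.

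This is a substantive amendment, because the population changes.

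On either route, check the consent form, which was not among the documents reviewed, against the chosen window.
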